METHODS: This is a monocentric, three-arm, controlled, randomized interventional study for patients with myotonic dystrophy type 1. The patient is not blinded regarding his therapy. The patient must provide informed consent prior to performing any protocol-related procedure. Eligible patients will be randomized and either perform 
(a) a nine-month respiratory strength training of respiratory muscles; or(b) a nine-month respiratory endurance training of the respiratory muscles, or(c) no respiratory muscle training. Lung function tests (FVC, FEV1, MIP, MEP), capillary blood gas analysis (pO ₂ , pCO ₂ , pH, Hb), 6-minute walking tests including oxygen saturation and patient questionnaires on quality of life and respiratory symptoms will be performed on scheduled visits throughout the treatment period. Adverse events (AEs) and concomitant medications / therapies are continuously monitored throughout the whole study period. Patients who are withdrawn from the trial for safety reasons or who withdraw their participation will not be replaced (i.e. a patient's study number will not be reused); however, it is planned to recruit additional patients if patients terminate participation prematurely.
NUMBER OF PATIENTS: A total of 45 patients are planned to be enrolled in the study. 15 patients per group will be randomized by the MUSCULAR IMPAIRMENT RATING SCALE (MIRS), age and gender.
INCLUSION- AND EXCLUSION CRITERIA: Inclusion criteria: A patient must meet all of the following criteria to be eligible for this study: 
1. the patient is willing and able to provide signed informed consent.2. the patient is ≥ 18 years old.3. the diagnosis of myotonic dystrophy type 1 has been confirmed by molecular genetics.

4. the patient is able and willing to perform pulmonary function tests (PFT) and blood sampling for capillary blood gas analysis (pO₂, pCO₂) throughout the study, to fill in a diary and to complete questionnaires.

Exclusion criteria:

A patient who meets one of the following criteria will be excluded from this study or not randomized to the study:

1. the patient requires invasive ventilation (non-invasive ventilation is allowed).
2. the patient uses non-invasive ventilation longer than 16h/day.
3. the patient participates in another clinical trial where therapy is provided.
4. the patient cannot perform pulmonary function tests (PFT).

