All patients who participate in this study will be included in the analysis. Data collected in this study will be documented using summary tables, figures, and patient data listings. For continuous variables, descriptive statistics (n, mean, median, standard deviation, minimum, and maximum) will be presented. For categorical variables, frequencies and percentages will be presented. Graphical displays will be presented as appropriate.

Power and Sample Size:

This is an exploratory study about efficacy and safety of respiratory muscle training in patients with Myotonic Dystrophy Type 1 and is not powered to make other statistical inferences.

Analysis-Sets:

Full Analysis Set: This analysis set consists of all patients who performed respiratory muscle therapy for at least 9 months or who did the check-ups throughout the 9 months without respiratory muscle training. All analyses will be based on this analysis set

Demographics and Baseline Characteristics:

Demographic and baseline data on medical/surgical history and disease history including length of repeats will be summarized using descriptive statistics for continuous variables and frequency distribution for categorical variables.

Safety:

A deterioration of >15% of FVC in comparison with baseline measurements will be defined as an AE, as well as developing unusual myalgia of respiratory muscles for more than 12 hours. The Adverse events will be collected from enrollment (=signed informed consent) through month 9 plus 7 days. Adverse events will be coded using the Medical Dictionary for Regulatory Activities, and categorized by system organ class and preferred term. All AEs will be displayed in patient listings. Adverse events will be categorized and tabulated for the treatment group overall by severity, seriousness, and relationship to study treatment

Efficacy:

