7 INVESTIGATIONAL PLAN

This is a monocentric, three-arm, controlled interventional study for patients with myotonic dystrophy type 1. The patient is not blinded regarding his group assignment (group 1 and 2: respiratory muscle therapy, group 3 control group without respiratory muscle therapy). The patient must provide signed informed consent prior to the study. Suitable patients will either perform

- (a) A nine-month strength training of respiratory muscles (group 1: strength training); or
- (b) A nine-month endurance training of the respiratory muscles (group 2: endurance training);
- (c) Or will not perform any respiratory muscle training for nine months (Group 3: control group).

Lung function tests (FVC, FEV1, MIP, MEP), capillary blood gas analysis (pO₂, pCO₂), 6-minute walking tests, oxygen saturation, and patient questionnaires on quality of life and respiratory symptoms are performed on scheduled visits throughout the entire treatment period. Adverse events (AE) and concomitant medication / therapies will continuously be monitored throughout the whole study. Patients who must be excluded from the trial for safety reasons or who withdraw their participation will not be replaced (i.e. a patient's study number will not be reused); however, it is planned to recruit additional patients if patients terminate participation prematurely.

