7.6 Training Discontinuation

A patient's study participation may be discontinued at any time at the patient's request or at the discretion of the Investigator. The following may be justifiable reasons for the Investigator to discontinue a patient from treatment:

- The patient was erroneously included in the study (i.e., was found to not have met the inclusion/exclusion criterion).
- The patient experiences an intolerable or unacceptable AE.
- The patient is unable to comply with the requirements of the protocol.
- The patient participates in another investigational study without the prior written authorization of the investigator.
- The patient becomes lost to follow-up.

Discontinuation of treatment does not imply withdrawal from the study, if applicable, the patient is suitable for admission to the control group. The investigator will document the reason(s) for treatment discontinuation on the CRF. Additional patients may be enrolled to offset effects of premature discontinuations.

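### The Full Analysis Set leaves out trained patients who stop before nine months, and Section 7.6 leaves open which group they then belong to

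*Protocol*

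**What the plan says.** **Analysis set.** The Protocol synopsis (Statistical Methods, Analysis-Sets) defines one set, the Full Analysis Set. Its first condition reads: "This analysis set consists of all patients who performed respiratory muscle therapy for at least 9 months". The second condition, the alternative for patients who do not train, admits those "who did the check-ups throughout the 9 months without respiratory muscle training". The synopsis bases every analysis on that set and names no separate safety set. Section 10 gives no other definition. The first sentence of the synopsis Statistical Methods, however, commits to including all participants.

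**Stopping training.** Section 7.6 lists reasons for ending treatment, among them: "The patient experiences an intolerable or unacceptable AE". It then states: "Discontinuation of treatment does not imply withdrawal from the study, if applicable, the patient is suitable for admission to the control group".

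**Control group.** Section 7 describes the third option for a randomised patient as follows: "Or will not perform any respiratory muscle training for nine months (Group 3: control group").

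**Safety.** Section 7.2.1 makes routine safety assessments the primary endpoints. Section 8.4 names FVC, FEV1, MIP and MEP among the safety parameters. It promises safety assessment for every enrolled patient until seven days after the month 9 visit.

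**The concern.** The analysis set selects on tolerance of training, which is close to the question that the primary objective asks. Patients who stop because of harm say most about whether lung function recovers or keeps falling. If they are outside the set, the training-arm summaries describe only patients who could train for nine months.

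Section 7.6 adds a second uncertainty. It rightly separates stopping training from leaving the study. It then mentions admission to the control group without saying whether this concerns follow-up only or also group membership. A patient who has already trained cannot fit the Section 7 description of group 3. Nothing in the Protocol says that such a patient is summarised in the group to which he or she was randomised.

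**Working it through.** **1. Does an early stopper fit the set?** Take a patient randomised to strength training who trains for one month, stops for an adverse event and attends every later visit.
- First condition (nine months of training): not met, with one month done.
- Second condition (nine months of check-ups without training): not met as written, because one of those months included training.

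The patient is therefore outside the only defined set, although the synopsis also says that all participants are analysed and Section 8.4 covers all enrolled patients. The statements cannot all be followed.

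**2. Effect on an arm's mean change.** The plan (synopsis, Efficacy; Section 10.6) summarises change from baseline with 95% confidence intervals. The Protocol states no expected stopping rate or size of fall, so these are assumptions. Let n = 15 per arm (Section 7.8), k = patients who stop, s = their mean FVC change and m = the completers' mean change, both in percent of baseline.
- As randomised: [(n - k)m + ks]/n
- Stated set: m
- Difference (as randomised minus stated set): k(s - m)/n

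With k = 3, s = -20 and m = 0, the as-randomised mean is 3 × (-20)/15 = -4.0 points. In the stated set it is 0, from 12 patients. With m = 0 throughout:

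| Assumed FVC fall in stoppers | k = 1, as randomised | k = 3, as randomised | Stated set |
|---|---|---|---|
| 16% | -1.1 | -3.2 | 0 |
| 20% | -1.3 | -4.0 | 0 |
| 30% | -2.0 | -6.0 | 0 |

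If three extra patients are enrolled to offset the three who stopped, as Section 7.6 allows, and they do not change, the as-randomised figure at a 20% fall is 3 × (-20)/18 = -3.3. The stated set still shows 0, now from 15 patients.

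**3. Effect on the proportion who stop for harm.** With 3 of 15 stopping, the rate as randomised is 20.0% (exact 95% CI 4.3% to 48.1%). In the stated set it is 0/12 by construction (0% to 26.5%).

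**4. How likely is at least one such patient?** Among 30 trained patients the chance is 1 - (1 - p)^30. For assumed rates p of 5%, 10% and 20% this gives 79%, 96% and more than 99%.

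**5. Follow-up under the mild reading of Section 7.6.** Appendix A schedules PFT, MIP and MEP at months 0, 1, 3, 5, 7 and 9 in groups 1 and 2, but at months 0, 5 and 9 in group 3. If admission to control means only moving to the group 3 schedule, the visits that remain are:

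| Stop after month | Own schedule | Group 3 schedule |
|---|---|---|
| 1 | 4 | 2 |
| 3 | 3 | 2 |
| 5 | 2 | 1 |
| 7 | 1 | 1 |

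Adverse-event checks are the same in both tables. Section 10.8 plans no imputation, so lung-function values not measured are not recovered.

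**The case against.** **Harms are still reported.** Section 9 lists adverse events for all patients, lists withdrawals due to adverse events separately, and summarises events that lead to study discontinuation. An FVC fall above 15% is itself an adverse event, so each patient in the illustration would appear in the listings. Section 10.4 accounts for all enrolled patients with reasons for discontinuation. This stands: a reader might infer that harms disappear from the report, and they do not. It does not repair the group-level lung-function summaries. Moreover, the separate listing concerns patients who leave the study, whereas Section 7.6 keeps those who only stop training in it.

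**The control-group clause is conditional.** It can mean follow-up without training. This also stands. A reader might infer that stoppers are to be analysed as controls, so that their decline is counted in the untrained arm. The Protocol does not say so, and the literal second condition of the set would exclude them even after admission to control. The text is unclear; it is not a demonstrated reallocation rule.

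**Wording on leaving the trial.** A reader might also take "Patients who must be excluded from the trial for safety reasons or who withdraw their participation will not be replaced", and the parallel synopsis sentence, to mean that stopping training for safety ends participation. Those sentences concern replacement and reuse of study numbers and set no such rule. The opening of Section 7.6, "A patient's study participation may be discontinued at any time at the patient's request or at the discretion of the Investigator", permits ending participation but does not require it.

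**The study is an exploratory pilot.** Section 10.1 plans no inferential tests, and no between-arm FVC difference is specified. The consequence is therefore a biased description within an arm, not a distorted test.

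**Conclusion.** The point holds in a limited form. Followed as written, the set leaves early stoppers out of the group summaries of FVC, FEV1, MIP and MEP, against two other statements in the Protocol. Section 7.6 leaves their group membership open. The Protocol itself fixes the set in conflict with its own text, so this is not a detail left to a later analysis plan.

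The size depends on how many stop and how far they differ from completers. With 1 to 3 of 15 stopping, falls of 16% to 30% and no change in the others, the arm mean shifts by about 1 to 6 points. If stoppers fare like completers (s = m), the mean does not shift. If they stop because they deteriorated, the stated set makes training look safer than it was. The stopping numbers and the falls are assumptions, and the as-randomised figures also require that FVC is measured in patients after they stop. The matter should be corrected, but it does not invalidate the trial.

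**What to change.** 1. **Section 7.6.** Delete the clause on admission to the control group. State that a patient who stops training, for safety or otherwise, stays in the randomised group for follow-up and analysis. The patient attends that group's remaining Appendix A visits unless consent is withdrawn, the patient is lost to follow-up, or the investigator ends participation under Section 7.2.4.
2. **Synopsis, Analysis-Sets.** Define the Full Analysis Set as all randomised patients in their randomised group, with no minimum duration of training. Use all enrolled patients for safety, with group summaries by randomised group. Keep the nine-month completers as a secondary set.

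The cost is a protocol amendment with ethics approval (Section 11.2) and modest effort to retain and test patients who have stopped training. No new visits are needed, because each group's schedule is already in Appendix A.

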7.7 Prior and Concomitant Medications and Therapeutic Procedures

Medications and therapies taken by the patient during the course of the study will be recorded in the Concomitant Medication CRF and Concomitant Therapies CRF, respectively.

7.8 Blinding and Randomization

This is a controlled, randomized, three-arm interventional study on the safety and efficacy of repetitive respiratory muscle training in patients with myotonic dystrophy type 1. As the disease is quite rare and the study is performed as pilot study, with 15 patients included in each group. The randomization software "Randoulette" of the LMU Munich is used for the randomization. The patients will be randomized in 3 groups of 15 patients each, age-, gender- and symptom-corrected according to the MUSCULAR IMPAIRMENT RATING SCALE (MIRS).

7.9 Therapy Compliance

The patient's compliance is monitored by a patient's diary, digital recording of the respiratory therapy device, and a successful performance of lung function testing. Missed or incomplete respiratory muscle training or function tests are clearly documented and considered in the analysis.

8 EFFICACY ASSESSMENTS

8.1 Study Schedule of Events

The study will be conducted as outlined in the following sections. Appendix A summarizes the study events at each visit.

8.2 Demographic and Screening Assessments

The patient's medical/surgical history and DM disease history including molecular genetics will be obtained to determine the patient's eligibility for the study, per inclusion and exclusion criteria in Section 7, prior to randomization. Demographic data, height, and weight will also be recorded at the Screening visit.

8.3 Efficacy Assessments

The efficacy of training will be evaluated using results from lung function tests (FVC, FEV1, MIP, MEP), capillary blood gas analysis (pH, pCO₂, pO₂), functional assessments (6-minute walk test, oxygen saturation and Borg scale), and questionnaires on quality of life and symptoms of respiratory failure.

8.3.1 Physical Examination

A complete physical examination will be conducted at the time points specified in Appendix A. The examination will include an assessment of the patient's general appearance; skin; head, eyes, ears, nose, and throat; examinations of lymph nodes, heart, lungs, abdomen, extremities/joints, neurological, mental status, and reflexes. Whenever possible, the same physician should perform the examination at each study visit. Any clinically significant abnormal findings that meet the definition of an AE per Section 8 and 9 (e.g., that result in an alteration in medical care, diagnostic or therapeutic) will be recorded on the AE page of the pCRF. The Investigator will continue to monitor the patient until the parameter returns to baseline or until the Investigator determines that follow-up is no longer medically necessary.

8.3.2 Vital signs

Vital signs (blood pressure, heart rate, respiratory rate, and temperature) will be taken prior to and after the performance of the 6MWT. Any clinically significant abnormal findings that meet the definition of an AE per Section 8 and 9 (e.g., that result in an alteration in medical care, diagnostic or therapeutic) will be recorded on the AE page of the pCRF. The Investigator will continue to monitor the patient until the parameter returns to baseline or until the Investigator determines that follow-up is no longer medically necessary.

8.3.3 Pulmonary Function Testing

PFT will be performed at time points specified in Appendix A. The PFT administration protocol will be standardized in accordance with the American Thoracic Society (ATS) guidelines (American Thoracic Society/European Respiratory 2002). PFT will include the assessment of

forced vital capacity (FVC), forced expiratory volume in the 1st second of the FVC maneuver (FEV1), maximal inspiratory pressure (MIP), maximal expiratory pressure (MEP), and peak expiratory flow (PEF) in the upright and supine positions.

FVC is the maximal volume of gas that can be exhaled with the patient breathing forcefully to obtain maximal airflow rates. For this measurement, the patient is instructed to inspire completely until the lungs are fully inflated. A nose clip is used to prevent leakage. Then the patient exhales as far as possible until the lungs are almost empty and the measured volume is recorded. Data are reported in liters and percent of predicted normal values based on age, gender, race, and height (Hankinson, Odencrantz et al. 1999).

Respiratory status will be assessed by spirometry using the KoKo PFT System © 2010 nSpire Health Inc. spirometer. FVC and FEV1 will both be measured in upright and supine position. In addition, the function of the respiratory muscles will be evaluated by the maximal respiratory pressures MIP for maximum inspiratory pressure and MEP for maximum expiratory pressure. For MIP and MEP in upright position, the CareFusion digital manometer from microRPM™ will be used with a flanged mouthpiece, as recommended by the American Thoracic Society (ATS) (American Thoracic Society/European Respiratory 2002). Calibration of software and spirometry devices will be done daily, as described in software manuals (Bolliger, Mathur et al. 2002).

8.3.4 Six minute walk test and Borg Scale

The six-minute walk test (6MWT) measures the distance an individual is able to walk over a total of six minutes on a hard, flat surface. The goal is for the individual to walk as far as possible in six minutes. The individual is allowed to self-pace and rest as needed as they traverse back and forth along a marked walkway. The 6MWT has been used with a variety of other conditions than chronic obstructive pulmonary disease (COPD) such as heart failure and stroke, and is widely used in neuromuscular diseases. The six-minute-walk-test will be conducted as recommended by the American Thoracic Society (American Thoracic Society/European Respiratory 2002) The Borg scale is a self-reported questionnaire designed to subjectively assess dyspnea and exertion during activity (Borg 1982). The Borg scale rates dyspnea on a scale of 0 to 10 incorporating nonlinear spacing of verbal descriptors of the level of intensity of dyspnea. A higher Borg score indicates more severe dyspnea. The Borg scale will be administered prior to starting the 6MWT (≤ 15 minutes) and after completing the 6MWT (≤ 5 minutes).

8.3.5 Patient-Questionnaires

8.3.5.1 DM1-Activ-c-questionnaire

This questionnaire explores the possible relationship between a patient's health status and the implementation of activities of daily life (ADL). The responses provide information on the extent to which the underlying myotonic dystrophy type 1 disease affects everyday and social activities, so that the extent of the limitations can be assessed. The questionnaire includes 25 questions, which are answered with the options 1-3 ("I am not able to do this", "...I am able to do it, but only with difficulties" and "...it is no problem for me") (Hermans, Faber et al. 2010).

8.3.5.2 FDSS

The Fatigue and Daytime Sleepiness Scale (FDSS) questionnaire is a questionnaire of 12 questions on daytime sleepiness and symptoms associated with sleep disorders. The FDSS consists of the topics ESS, DSS and FSS. The 12 items selected for the final FDSS scale met all

expectations of the Rasch model, and the hierarchy of items was invariant in DM1 patients of different age, gender, disease type, educational level and use of psychostimulants, as well as between patients from different countries (Hermans, Merkies et al. 2013).

8.3.5.3 Respicheck

The Respicheck questionnaire was developed at the 207th working session on respiratory insufficiency in myotonic dystrophies. This questionnaire is very simple and contains 27 Yes / No questions for nine groups of symptoms related to respiratory insufficiency (Sansone and Gagnon 2015).

8.3.6 Clinical Laboratory Tests (blood analysis)

At the initial examination and every two months a capillary blood analysis will be performed, using epoc blood analysis system, which consists of epoc® BGEM Test Card, epoc® Host2 Mobile Computer and epoc® Care-FillTM Capillary Tubes. Calibration will be done as recommended in users' manual. The Care-Fill™ Capillary Tubes are designed to collect a blood sample from a skin puncture. The tube fills with a blood sample through a combination of capillary action and gravity flow. When sufficient blood is present, the tube fills readily and preserves the integrity of the blood sample until it can be tested by preventing clotting and alteration of analytic concentrations. For each blood draw, approx. 90µl are needed for sufficient analysis. In total, approx. 540µl are drawn per patient during the whole study. The following parameters will be measured: pH, pCO2, pO2.

Observed measurements and changes from baseline to study time points in month 1,3,5,7 and 9 will be descriptively summarized. All laboratory values will be classified as normal, above normal, or below normal based on normal ranges provided by the laboratory. Frequencies of abnormal values and clinically significant abnormal values will be summarized. All data will be presented in listings along with individual listings of patients with clinically significant abnormal laboratory values.

